11.5.3. IND Annual Report to the FDA

The PI will be responsible for the preparation of a detailed annual synopsis of clinical activity, including AEs, for submission to the sponsor's representative [REDACTED]. Each annual report will summarize IND activity for 1 year beginning approximately 3 months before the IND FDA anniversary date. The sponsor's representative will notify the PI of the due date with sufficient time for the PI to assemble the required information.

11.5.4. Final Report

A final study report will be prepared in accordance with FDA's *Guidance for Industry: Submission of Abbreviated Reports and Synopses in Support of Marketing Applications* and ICH E3 Guideline *Structure and Content of Clinical Study Reports* and provided to the sponsor's representative for review and approval. The sponsor's representative will use this report to prepare the final clinical study report for submission to the FDA.

12. STATISTICS

12.1. Description of Statistical Methods

Detailed statistical procedures, listings, table shells, and figures will be provided in a separate statistical analysis plan (SAP).

This Phase 1 trial has two objectives:

- To characterize the safety and tolerability profile of ascending doses of Scopolamine HBT administered by IM injection (0.005mg/kg to 0.021mg/kg) and set upper limits on the probability of extreme and non-extreme DLTs across dosage levels
- To characterize the PK of ascending doses of Scopolamine HBT administered by IM injection and assess dose proportionality for C_{max} and AUC_{∞} over the dosing range

[Table 12](#) shows the study objectives and endpoints.

Table 12: Study Objectives and Endpoints

Study Objective	Study Endpoints
Safety	Extreme and nonextreme DLTs SAEs related to drug All AEs that are not SAEs Vitals signs, ECG, and clinical laboratory values and their changes from baseline Injection site assessments Clinically relevant physical exam findings Neuropsychiatric measures (BPRS, C-SSRS, and RASS) Cognitive measures (DSST)
Pharmacokinetics	C_{max} , T_{max} , $t_{1/2}$, V_d , F , Cl , MRT , $C_{max}/Dose$, $AUC_{\infty}/Dose$

Detailed descriptions of the endpoints and their measurements can be found in Section 10 and Section 11. Additional discussion of the statistical methodology and assumptions can be found in the SAP.

12.1.1. Pharmacokinetic Analysis

The PK analysis will be performed on the pharmacokinetics analysis set. Blood samples will be obtained for PK assessments prior to dosing and at 2, 5, 10, 15, 20, and 30 minutes and 1, 2, 4, 8, 12, 24, 36, and 48 hours post dose. Scopolamine HBT PK assessments will include

determination of the following parameters: observed C_{max} , T_{max} , V_d , $t_{1/2}$, Cl , AUC_{last} , AUC_{∞} , $C_{max}/Dose$, MRT, and $AUC_{\infty}/Dose$. Plasma concentration time profiles for each subject tested will be evaluated using semi-log plots and characterized using noncompartmental analysis (WinNonlin). PK data will also be summarized graphically by dose group. PK and safety endpoints will undergo PD analysis and evaluation.

Data for PK parameters will be summarized by group using descriptive statistics including mean, standard deviation, minimum, maximum, and may include median and quartiles. All PK data for individual participants will be provided in listings.

Dose proportionality will be tested for $C_{max}/Dose$ and $AUC_{\infty}/Dose$ using ANOVA models. Likelihood ratio tests will be used to test the joint hypothesis of equivalence across dose levels. Equivalence will be tested for each dose level against the next higher dose level. Equivalence of parameters across doses (dose equivalence) will be tested for T_{max} , $t_{1/2}$, V_d , and MRT. All ANOVA models of PK parameters will adjust for sex.

12.1.2. Safety Analyses

Safety analysis will include data collected from the safety analysis set. DLT and AE data will be coded using the current MedDRA version at the time of study setup, listed individually (including intervention and outcome), and summarized by system organ class and preferred terms within a body system for each treatment group. Data will be summarized by both event (counting each event regardless of subject) and by subject (counting only one event within each system organ class or preferred term). Serious and/or unexpected AEs will also be discussed on a case-by-case basis.

Changes in pulse rate, systolic and diastolic blood pressure, weight, and respiratory rate will be summarized (mean, median, minimum, maximum, standard deviation) by dose level and time point. Clinical laboratory assessment results will be presented.

Upper bounds of 80% confidence intervals of the true probability of events (extreme DLTs, non-extreme DLTs, and severe AEs) will be estimated from the number of events in each cohort using the Pearson-Clopper method.

Descriptive statistics of BPRS, C-SSRS, DSST, RASS (if conducted), and injection site VAS scores (mean, median, standard deviation, minimum, and maximum) will be presented for each dose level and time point.

Changes in the BPRS score (6 hours, 48 hours, and 8 days) from baseline will be compared between placebo and active dose levels using ANOVA models for each time point. The null hypothesis of no difference between placebo and the active dose will be tested for each dose level using a one-sided alternative hypothesis of higher increases among the participants receiving the active drug than among the placebo group.

Participants have C-SSRS scores of zero at baseline. The proportion of individuals having any increase in their C-SSRS score from zero will be compared for each drug dosage level to the placebo group using Fisher's exact test.

The DSST will be conducted at screening, Day -1, Day 3, and Day 8. Changes from baseline (Day -1) will be compared between placebo and active dose levels using ANOVA models for each time point. Placebo control will help to exclude any remaining practice effects or changes

unrelated to the study drug. The null hypothesis of no difference in DSST scores between active Scopolamine and placebo will be tested for each dose level using a one-sided alternative hypothesis of more negative changes in DSST scores among participants receiving the active drug than among the placebo group. A pooled analysis will compare all Scopolamine dosage levels to placebo. Individual participants' DSST scores will be presented by study day, and persistent declines in scores at Day 3 or Day 8 will be noted.

Frequencies of severity (None, Mild, Moderate, Severe, Potentially Life Threatening) from injection site assessments performed by clinicians will be summarized by type (pain, tenderness, erythema/redness, induration/swelling) and time point by dosage group. Semi-log graphs of mean VAS scores will be plotted (VAS score vs. log-time since injection). Differences between placebo and active drug injection site VAS scores will be compared statistically by dosage level using 3 different ANOVA models corresponding to the first hour, next 4 hours, and 8-48 hours after injection. A Wald test with a one-sided alternative will be used.

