
Continuous cardiovascular monitoring of ECG (3-lead) and vital signs (systolic and diastolic blood pressure (at 5-15 minute intervals), heart rate, respiration rate, and pulse oximetry) will be performed from 1 hour prior to and for 24 hours following Scopolamine HBT or placebo administration. During the first 24 hours and through 48 hours post dose, vital sign monitoring (including body temperature), 12-lead ECG, clinical assessment of neuropsychiatric status (using the BPRS, C-SSRS, and Richmond Agitation and Sedation Scale), and injection site reaction assessments will be performed and documented at specified times. The Digit Symbol Substitution Test will be administered prior to dosing and at 48 hours post dose and Day 8 to detect any persistent cognitive effects. Standard serum chemistry, hematology, and urinalysis testing will be performed at baseline (Day-1), at 24 and 48 hours post dose, and at Day 8. Subjects will be monitored for AEs continuously while in clinic, and AEs will be documented as they are reported. Follow-up for AEs will be conducted via telephone on Days 4 and 30, and via an in-clinic visit on Day 8 unless otherwise reported by the subject. In the event of a potential AE, additional

assessments/testing may be performed if, in the judgment of the investigator or designee, they are warranted for the safety of the subject. AEs will be followed until resolution/stabilization.

Statistical Methods:

Results of safety assessments will be summarized across dosing levels and compared to the placebo group. AEs will be listed by treatment group and body system using MedDRA terms. Confidence intervals for the probability of dose-limiting toxicities and severe adverse events will be estimated based on the number of observed events in each dosing cohort. Scores for injection site assessments, and changes in cognitive and neuropsychiatric scales will be compared for each dosage level relative to placebo. Plasma concentration curves will be fit using noncompartmental analysis to obtain PK parameters for each dosing cohort prior to dosage escalation. PK parameters will be summarized by dosage level, and the parameters C_{max} and AUC_{∞} will be tested statistically for dose proportionality.

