ICH	International Conference on Harmonisation of Technical Requirements for Registration of Pharmaceuticals for Human Use
IM	Intramuscular
IND	Investigational New Drug
IV	Intravenous
Kg	Kilogram
L	Liter
MedDRA	Medical Dictionary for Regulatory Activities
Min	Minute
mL	milliliter
MRT	Mean Residence Time
PD	Pharmacodynamics
PI	Principal Investigator
PK	Pharmacokinetics
PR interval	Time between P and R waves
██████████	██████████
QRS interval	Time between Q, R, and S waves
QTc	QT interval adjusted for heart rate
QTcF	QTc (Fridericia)

RASS	Richmond Agitation Sedation Scale
SAE	Sever Adverse Event
SAP	Statistical Analysis Plan
Scop HBT	Scopolamine Hydrobromide Trihydrate
SD	Study Day
Sec	Second
SEM	Standard Error of the Mean
Ng	Nanogram
$t_{1/2}$	Half life
TEAEs	Treatment-emergent Adverse Events
T_{max}	Time to maximum concentration
VAS	Visual Analog Scale
V_d/F	Apparent Volume of Distribution
WHO	World Health Organization

Summary of Changes

Version	Change	Sections	Made By	Approved by
2.0	Updated personnel	Page 1-2	[REDACTED]	[REDACTED]
	Corrected typographical error	3.1	[REDACTED]	[REDACTED]
	Clarified references to protocol appendices	5.1.3.1 5.1.10	[REDACTED]	[REDACTED]
	Corrected references to other parts of the SAP	6.3	[REDACTED]	[REDACTED]
	Updated to clarify PK analysis will be presented in separate PK report	6.6.2	[REDACTED]	[REDACTED]
	Revised statistical modeling for PK parameters to better reflect the Protocol specified analyses.	6.3, 6.15	[REDACTED]	[REDACTED]
	Updated to add imputation rules for missing or partial dates for AEs and concomitant medications	6.6.3	[REDACTED]	[REDACTED]
	Updated to remove figures based on discussion and agreement from client Biostatistician. No figure shells will be provided.	5.1.9, 6.2 6.14.2, 6.14.3, 6.14.4, 6.14.6, 6.14.8, 6.18	[REDACTED]	[REDACTED]
	Add Table and Listing shells.	Table and Listing Shells	[REDACTED]	[REDACTED]

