5. ENDPOINTS AND COVARIATES

5.1 SAFETY ENDPOINTS

The first objective of this study is to characterize the safety of Scop HBT at varying dosages. The study specifically defines three types of safety endpoints in the protocol: extreme dose-limiting toxicities (DLTs), nonextreme DLTs, and serious adverse events (SAEs) related to the drug. Any events or issues not defined as extreme/nonextreme DLTs or SAEs will be considered as Adverse Events (AEs). In addition to AEs, data will be collected and analyzed on injection site

assessments and changes in cognitive function, neuropsychiatric status, vital signs, clinical laboratory results, heart rhythm, and physical health status.

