6.4 UPPER-BOUND ESTIMATION FOR DLTs & SAEs

As part of the first objective, to characterize the safety and tolerability of Scop HBT IM injection at varying dosages, upper limits for the probability of an event at each dosage will be estimated using data on the occurrence of extreme DLTs, non-extreme DLTs, and SAE.

Dose progression follows rules that require dosing be halted if an extreme DLT or a SAE related to the drug occurs within any cohort. Therefore, the maximum number of extreme DLTs that can occur in a cohort prior to stopping is one. Should one nonextreme DLT occur in the first four participants or two in the first 8 participants, dosing will be halted. If dosing is resumed (upon determination of the PI, DSMB, and sponsor) and a second nonextreme DLT occurs among the first 4 in cohort or 3 total DLTs occur, dosing and enrollment will be halted.

Confidence intervals will be determined using 80% confidence interval, such that there is a 10% probability that the true value exceeds the upper-bound. The Pearson-Clopper interval is the most conservative among the binomial intervals, resulting in the highest upper confidence bounds.

Should no events of any type occur within a cohort, with 6 participants dosed, the 80% confidence interval upper bound for the probability of any event is 0.32. Should one extreme

DLT or SAE occur in any cohort, the upper bound for the SAE/extreme DLT will depend on the number dosed prior to the event occurring. Table 8 shows the upper bounds of confidence intervals based on the number of participants receiving active Scop HBT.

Table 8: Upper-bound estimates of Risk Inferred from Events in Cohort

		Number Receiving Active Scop HBT			
		2	4	6	9 ¹
Event Type	Number of Participants with Event	80% C.I. Upper Bound (Pearson-Clopper Method)			
No Events	0	N/A	N/A	0.32	N/A
Extreme DLT	1	0.95	0.68	0.51	0.37
Nonextreme DLT	1 of first 4 in a cohort, none thereafter	0.95	0.68	0.51	0.37
	2 in the first 8 in a cohort	1.0	0.86	0.67	N/A
	2 of the first 4 in a cohort	1.0	0.86	N/A	N/A
	3 in any cohort	N/A	0.97	0.80	0.60
SAE not already designated as a DLT (except unrelated)	1	1.0	0.68	0.51	0.37

¹If nonextreme DLT occurs in a given cohort, the cohort may be expanded to 12 participants, a maximum of 9 of whom will receive active Scop HBT.

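### The protocol specifies upper bounds for severe AEs but the SAP gives them for related serious AEs, so Grade 3 events that are neither serious nor DLTs get no bound

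*Protocol*

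**What the plan says.** **Protocol.** Section 12.1.2 sets the analysis: "Upper bounds of 80% confidence intervals of the true probability of events (extreme DLTs, non-extreme DLTs, and severe AEs) will be estimated", per cohort, by the Clopper-Pearson method. The synopsis agrees: "Confidence intervals for the probability of dose-limiting toxicities and severe adverse events will be estimated". The objective as worded in Section 12.1 is narrower and asks only to "set upper limits on the probability of extreme and non-extreme DLTs across dosage levels". Section 11.3.1 treats severity (a grade) and seriousness (an outcome) as different things. It requires Grade 4 and Grade 5 events to be reported as SAEs but makes no such rule for Grade 3, the severe grade.

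**SAP.** Section 6.4 says the bounds will be obtained "using data on the occurrence of extreme DLTs, non-extreme DLTs, and SAE". The matching row of Table 8 is labelled "SAE not already designated as a DLT (except unrelated", with the bracket then closed. Section 5.1 describes the third endpoint type as "nonextreme DLTs, and serious adverse events (SAEs) related to the drug", and Section 5.1.4 defines serious by outcome. The abbreviation list, however, expands SAE as "Sever Adverse Event".

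**Precedence.** SAP Section 1 says the SAP overrides the protocol where the two differ, and that differences will be described in SAP 6.2. Section 6.2 does not mention this one.

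**The concern.** Because the SAP takes precedence, following it means that a bound specified twice in the protocol is not produced and a bound on a different event set takes its place. The abbreviation list adds a practical risk: two programmers working from this SAP could fill the same row with different counts, one by severity and one by seriousness.

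The events affected are plausible in this trial. Under Protocol 7.6.1.1 and 7.6.1.2, neuropsychiatric symptoms such as delirium or hallucinations become DLTs if they need medication, or if BPRS thresholds are met at 48 hours. Severe sedation or disorientation that clears before 48 hours without medication matches none of the listed neuropsychiatric criteria, and nothing makes it automatically serious, although an investigator could judge it so.

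Protocol 5.2.4 describes a study of 1 mg IM (given there as 0.014 mg/kg, the Cohort 4 dose) in which healthy volunteers became disoriented, confused, uncoordinated and physically incapacitated. The same section cites an IM ED50 of 1.4 mg for general confusion. Cohort 5 gives 0.021 × 70 = 1.47 mg to the 70 kg subject used as reference in Protocol 5.2.2. These figures show that such events can occur. They do not give a Grade 3 rate.

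**Working it through.** **1. Reproduce Table 8.** The method is the exact upper limit of a two-sided 80% interval, which leaves 10% in the upper tail: U(x, n) = the 0.90 quantile of Beta(x + 1, n − x), with U = 1 when x = n. Two cases can be checked by hand:
- 0 of 6: 1 − 0.10^(1/6) = 0.319. The SAP prints 0.32. (A one-sided 80% limit would be 0.235, so the SAP is using the two-sided interval.)
- 1 of 2: the square root of 0.90 = 0.949. The SAP prints 0.95 in the DLT rows.

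| Events / active | Computed | Table 8 |
|---|---|---|
| 0/6 | 0.319 | 0.32 |
| 1/2 | 0.949 | 0.95 (DLT rows); **1.0 (SAE row)** |
| 1/4 | 0.680 | 0.68 |
| 1/6 | 0.510 | 0.51 |
| 1/9 | 0.368 | 0.37 |
| 2/2 | 1.0 | 1.0 |
| 2/4 | 0.857 | 0.86 |
| 2/6 | 0.667 | 0.67 |
| 3/4 | 0.974 | 0.97 |
| 3/6 | 0.799 | 0.80 |
| 3/9 | 0.599 | 0.60 |

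Every entry reproduces except one: the SAE row prints 1.0 for 1 event in 2 subjects, where the same calculation gives 0.95.

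**2. Compare the event sets.**

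| Event in an active subject | Bound in SAP Table 8? | In the protocol's severe-AE bound? |
|---|---|---|
| Grade 3 or higher, meets a DLT criterion (for example a severe injection site reaction) | Yes, as a DLT | Yes |
| Grade 3 or higher, related SAE, not a DLT | Yes, in the SAE row | Yes |
| Grade 3, not serious, not a DLT | **No** | **Yes** |
| Grade 3 or higher, unrelated SAE, not a DLT | No | Yes (no relatedness limit is stated) |
| Grade 1 or 2, related SAE, not a DLT | Yes, in the SAE row | No |

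Neither set contains the other. The third line is the main gap. SAP 6.14.5 tabulates those events by maximum severity for each cohort and dose level, without an interval.

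**3. Size of the gap.** The documents give no severe-AE rate, so the full range is shown, with the same formula and x = number of active subjects with at least one Grade 3 or higher AE.

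| x | n = 6 | n = 9 |
|---|---|---|
| 0 | 0.319 | 0.226 |
| 1 | 0.510 | 0.368 |
| 2 | 0.667 | 0.490 |
| 3 | 0.799 | 0.599 |
| 4 | 0.907 | 0.699 |
| 5 | 0.983 | 0.790 |
| 6 | 1.0 | 0.871 |

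Illustration: 6 active subjects, no DLT and no SAE. The SAP reports only the zero-event bound, 0.32. If 2 of the 6 had a Grade 3 AE that was neither serious nor a DLT, the protocol's severe-AE bound would be 0.67; if 3 of the 6, it would be 0.80.

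**The case against.** **The protocol's word may itself be the slip.** The Section 12.1 objective asks for limits on DLTs only. Protocol Table 12 lists drug-related SAEs and has no separate severe-AE endpoint. The halting rules in Protocol Table 6 use extreme DLTs, nonextreme DLTs and SAEs, and SAP Table 8 follows those rows. The misspelt abbreviation also points to confusion of terms. This stands as far as intent goes: a reader might infer that the SAP deliberately dropped a severe-AE analysis, and the documents do not show that. It does not remove the conflict, because the protocol says severe in two places and the governing document says something else without recording it.

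**Many severe events are already bounded.** A reader might infer that every non-serious Grade 3 event loses its bound. That is not so. Severe injection site reactions, and neuropsychiatric symptoms that need medication, are DLTs and are covered by those rows. If any of the Grade 3 events in the illustration were DLTs, a DLT row would already be above 0.32.

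**These events do not limit dosing.** A reader might also take the unbounded events for the likeliest dose-limiting signal. Protocol 7.6.1 defines halting through DLTs and related SAEs, together with clinical judgment, and each of those event classes has a bound.

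**The consequence is small.** Grade 3 counts with their denominators will be reported, so anyone can compute the interval from them. Protocol 12.3 and SAP 6.7.2 confirm that the DSMB uses no statistical test to halt or terminate. This stands, and it keeps the point modest.

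**Conclusion.** The point holds in a limited form. Protocol and SAP specify different event sets for the third upper bound, the difference is not recorded where the SAP says it will be, and the SAP's abbreviation list leaves the term ambiguous. The result is that Grade 3 AEs that are neither serious nor DLTs get counts but no upper bound.

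The illustrative gap of 0.32 against 0.67 or 0.80 rests on three assumptions: 6 active subjects, no DLT and no SAE in the cohort, and 2 or 3 subjects with such a Grade 3 AE. The last is hypothetical. Severe is read as Grade 3 or higher; the protocol does not spell this out for the bound. What is missing is a protocol-specified descriptive interval. Neither the underlying data nor the conduct of dose escalation is affected. It should be corrected before unblinding, while the change can still be recorded as pre-specified.

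**What to change.** Reconcile the event set so that the two documents agree:

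1. In SAP 6.4 and Table 8, add a row for each dose giving the 80% Clopper-Pearson upper bound for subjects with at least one Grade 3 or higher AE. State that it counts all such subjects, regardless of DLT, SAE or relatedness status, so that its overlap with the other rows is clear.
2. Keep the related-SAE row, and record it in SAP 6.2 as an addition to the protocol's analyses.
3. Correct the abbreviation list so that SAE reads Serious Adverse Event.
4. In the SAE row of Table 8, change the entry for 1 event in 2 subjects from 1.0 to 0.95.

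If the sponsor meant serious all along, amending Protocol 12.1.2 and the synopsis would also remove the conflict. Adding the row is preferable because it delivers what the protocol already specifies.

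The cost is SAP wording and one more descriptive row that overlaps the DLT rows. No new data and no new method are needed.

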12.1.3. Clinical Laboratory Data Analyses

For hematology and serum chemistry tests, the median, mean, standard deviation, minimum, and maximum of all values for each test within each treatment group at baseline and for all raw values and change for baseline for subsequent time points will be provided in a summary table. A second table (a "shift table") will be made, showing for each laboratory variable the percentage of subjects in each treatment group whose values decreased, stayed the same, or increased between the baseline or pretreatment period and the subsequent visits. A third table will be prepared displaying the numbers of subjects in each treatment group who had values below, within, and above the normal range at baseline and at subsequent time points.

These tables will be reviewed by the PI or research monitor to evaluate whether any significant trends in laboratory values occurred. The PI or research monitor will also review urinalysis data by inspecting the laboratory data tabulations, but no summary tables of these will be prepared.

